Over the years various improvements have been made to better stratify the risk for complications in the pre-and intra-operative setting. Vital signs are collected pre-operative and continuously during surgery. Postoperative monitoring at the hospital ward consist of three spot checks a day and consists of heart rate, respiratory rate, oxygen saturation, blood pressure, temperature and pain scores. These parameters are scored and displayed as an overall EWS score. Technological developments introduced possibilities to electrify some of these vital parameter measurements with enhanced accuracy as a result (5, 15, 22). The original EWS system was, based on new insights, improved and replaced for the modified EWS (MEWS) which included oxygen saturation and the national EWS (NEWS) which included oxygen saturation (20, 21). Despite these advances, EWS methodological outcomes are moderate and discrimination is poor in daily practise (2, 3). Additionally, the application of many different subtypes is widespread and validation studies contain methodological and reporting shortcomings (2, 3). These factors question the clinical reliability of EWS and require a development regarding monitoring methods.

In the Catharina hospital, two studies were conducted with the Philips Healthdot, the PEACH (16) study and the TRICA study (15, 17). The TRICA study, performed at the surgical department, contributed to the CE-marking of the Healthdot as a monitoring device. The PEACH study has investigated outpatient monitoring after bariatric surgery with a positive result(15, 17).

With the transition to surgery in ambulatory setting, accelerated by the COVID-19 pandemic, the hospitalized patients are older, have more comorbidities and are therefore more prone to complications. Early vital sign alterations such as tachypnoea and tachycardia are common underdiagnosed in post-operative surgery patients (22). Automated monitoring is able to identify these micro-events and thereby offers the potential to improve ward monitoring and the medical care (22).

The application of smart monitoring devices as a solution for these limitations is a hot topic within the transition of care. Many domestic and international study groups have demonstrated the effectiveness of a smart monitoring sensor in improved patient monitoring on the hospital ward (5, 14, 23-25).

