6. INVESTIGATIONAL PRODUCT

a. Name and description of investigational product(s)

The Healthdot is a CE marked wearable data logger (15, 17). It consists of an adhesive layer, electronics and a battery. The intern mechanism contains an accelerometer which is able to measure movement including movement of the lung and heart. This movement data is processed with a validated algorithm to calculate heart rate, respiratory rate, posture and physical activity which are stored on the device and transferred through the LoRa network via the local gateway and/or gateways provided by KPN. The entire technological infrastructure system consists of:

- 1. Healthdot
- 2. Gateway
- 3. KPN-LoRa network
- 4. Server
- 5. Guardian dashboard

Required training

The investigators, nursing staff and physicians will receive a training and e-learning during the pre-implementation phase about the application of the Healthdot, the activation sequence and data reading. In addition, the structure of the study with the questionnaires, the timetable, the procedures in cases of malfunctions/ ADEs will be provided in a protocol.

Contra-indications

- Known to have severe allergy for the tissue adhesive used in the Healthdot.
- Any skin condition, for example prior severe rash, discoloration, scars or open wounds at the area of application
- Pregnant, or breastfeeding
- Use of topical that is known to influence the skin at the test area (such as medical and nonmedical creams or lotions)
- Patient with active implantables such as Implantable Cardioverter Defibrillator (ICD) and pacemaker

SWITCH - Surgical Ward Innovation: Telemonitored controlled by Healthdot

Evaluation of implementation

- Unable to understand instructions
- Left lower rib (place where Healthdot will be applied) is involved in the area of surgery, area of disinfection or area where bandages are needed.
- Transfer to a different ward during hospitalization

Indications for switching Healthdot

- No successful measurement after 4 hours or earlier if clinically necessary.
- When the Healthdot is not connected within 60 min after application

Indications to remove the Healthdot

• In case that an exclusion criterion is met during the study

b. Summary of findings from non-clinical studies

Research into the implementation of a new technology in healthcare can only be investigated in a clinical setting. No non-clinical studies are therefore contributing.

c. Summary of known and potential risks and benefits

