7. METHODS

a. Study parameters/endpoints

i. Main study parameter/endpoint

Primary parameters and endpoints

Evaluation of the implementation of a continuous monitoring method on the surgical ward

- Fidelity: The usability and degree of implementation of the Healthdot at the surgical ward
 - Measured with the System usability scale (SUS), Score > 68 at M6 (8, 26)

- Acceptability: The workload regarding the amount of spot checks in addition to the standard monitoring.
 - Calculated with data from the electronic patient file records. Success in case of average reduction of 20% at M6 compared to M3

ii. Secondary study parameters/endpoints (if applicable)

Secondary parameter and endpoints

- Adoption: The intention and attitude towards the use of the Healthdot monitoring method.
 - Measured with evidence-based practise attitude scale (EBPAS) (9, 10).
- Feasibility: The extent to which the Healthdot monitoring method can be successfully carried out by the healthcare employees.
 - Measured with a thematic analysis (Braun and Clark) with core group (11).
- Acceptability: Amount of manual spot checks per hospital admission day per patient
 - \circ Calculated with data from the electronic patient file records.
- Acceptability: The perception among nursing staff given the satisfactory and agreeableness regarding workload.
 - Measured with the integrated workload scale (IWS) (12, 13).
- Appropriateness: Relation between device false alarms (noise) and correct alarms based on the alarming protocol.
 - Measured as signal to noise ratio (SNR)
- Appropriateness: Number of unexpected events that occur during or result from the use of the Healthdot medical device. Measured as adverse device events (ADE)
- Feasibility: The amount of time needed to perform and process a complete manual spot check or digital monitoring check. Measured manually.
- Costs: Cost-effectiveness analysis based on the duration of admission, the associated admission costs and the monitoring method
- Advanced algorithm analyses for improved monitoring protocols with advanced AI software

iii. Other study parameters (if applicable)

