During the first phase, the daily output will consist of:

• 3x daily spot check according to the hospital protocol where the vital values are manually entered in the electronic patient file and scored with EWS. In addition, the Healthdot will be applied for training purposes. Data from the Healthdot during this phase will not be used in clinical care.

Alarmsignalen bij vitaal bedreigde patiënt 2							
EWS Score	3	2	1	0	1	2	3
Hartfrequentie		<40	40-50	51-100	101-110	111-130	>130
Bloeddruk (syst)	<70	70-80	81-100	101-200		>200	
Ademfrequentie		<9		9-14	15-20	21-30	>30
Temperatuur		<35,1	35,1-36,5	36,6-37,5	>37,5		
Bewustzijn				Α	v	Р	U
A = Alert V = Reactie op aanspreken P = Reactie op pijn U = Geen reactie							
Wanneer u ongerust bent over de conditie van de patiënt: I punt extra							
Wanneer de urineproductie <75 ml gedurende de afgelopen 4 uur: I punt extra SIT:							
Indien de saturatie <	90 ondanks	therapie: ->	3 punten			sein 1	[name]

Table 2: Current (M)EWS protocol at the Catharina hospital for ward monitoring

During phase 2, the Healthdot is the primary monitoring method. Each patient admitted to the surgical ward will receive the Healthdot during intake until discharge. In case the hospitalization duration is longer than the battery life, approximately 14 days, the Healthdot will be replaced by a new device. The Healthdot measures heart rate, respiration rate and physical activity every 5 minutes. These parameters are displayed in the Guardian dashboard as a trendline and automatically transferred to the electronic patient file 3 times a day (08u,12u,17u). These measurements are scored in accordance with the alarm protocol and, if necessary, provide a notification. In case of an additional measurement, a spot check will be performed by the nursing staff.

The protocol alarms in case the respiration rate is above 20/min and or the heart rate is 110 or more for 15 minutes consecutive.

Score	0	+1	+2] [CREWS	
Vital parameter							
Heart rate	<110		≥110		0-1	2	3
Respiration rate	<20	≥20					

Table 3: New CREWS protocol for monitoring with Healhtdot on the ward

Indications for spot check monitoring

- Based on previous research, the Healthdot measurements can be relied upon, and no additional spot check monitoring will be routinely necessary for respiration and heart rate unless clinical doubt about the obtained value.

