- Additional spot check monitoring for blood pressure, oxygen saturation and temperature may be requested by any member of the treatment team

Premature termination of the study

• In the event that the International Workload Scale (IWS) (13) is in the highest category at moment 4-5 for more than 50% of the staff.

d. Withdrawal of individual subjects

Subjects of the core group can leave the study at any time for any reason if they wish to do so without any consequences.

i. Replacement of individual subjects after withdrawal

Participants who withdraw their participation from the core group won't be replaced.

e. Follow-up of subjects withdrawn from treatment

N/A

f. Premature termination of the study

In case the International Workload Scale (IWS) will be in the highest category of this scale for more than 50% of the staff at month 4-5 during phase two of this project.

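### The time endpoint sets a complete manual spot check beside an undefined digital check covering two of its six items, so an unknown, possibly large part of any difference may not be efficiency

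*Combined protocol and SAP*

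**What the plan says.** The Summary and section 7.a.ii list as a secondary feasibility endpoint "The amount of time needed to perform and process a complete manual spot check or digital monitoring check", measured manually. The measurement timetable in section 3 marks it in months 1 to 6, and Table 4 in section 8 assigns it descriptive statistics. There is no success threshold, no planned number of timed checks and no expected duration.

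On the manual side, section 1 says that ward monitoring "consists of heart rate, respiratory rate, oxygen saturation, blood pressure, temperature and pain scores", three times a day. Section 7.c adds that in phase 1 "the vital values are manually entered in the electronic patient file and scored with EWS".

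On the digital side, section 7.c says "The Healthdot measures heart rate, respiration rate and physical activity every 5 minutes", with values "automatically transferred to the electronic patient file 3 times a day". Section 6.a adds posture to the device's output. The phase 2 score in section 7.c (Table 3) uses heart rate and respiration only.

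For the remaining parameters in phase 2, section 7.c says "Additional spot check monitoring for blood pressure, oxygen saturation and temperature may be requested by any member of the treatment team". Section 3 makes manual checks in that phase conditional on an indication.

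No section defines the digital monitoring check, says whether requested measurements are timed with it, or plans a split of the manual time by content.

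**The concern.** The two checks being timed do not have the same content. If the digital time is shorter, at least three things may have contributed: the device obtains heart rate and respiration with less work; values are transferred automatically instead of being typed in and scored; and other parameters are not taken at that moment. The first two are efficiency. The third is a change in what is measured, and some of its time may return later as a requested manual check.

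This matters because efficiency is part of the rationale in the Summary and of the primary hypothesis in section 2, and this is the only endpoint that measures staff time. The primary acceptability endpoint counts spot checks, and the IWS records perceived workload. With two descriptive durations and no test or threshold, readers will subtract one from the other and read the result as time gained.

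**Working it through.** **Step 1: content side by side.**

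| Item of the manual check (section 1) | Supplied by the Healthdot (6.a, 7.c) | Route in phase 2 (7.c) |
|---|---|---|
| Heart rate | yes | device |
| Respiratory rate | yes | device |
| Oxygen saturation | no | on request |
| Blood pressure | no | on request |
| Temperature | no | on request |
| Pain score | no | not stated |

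The overlap is 2 of 6 items; 4 of 6 (67%) are outside the device's output. The EWS table in section 7.c has a somewhat different set: it includes consciousness, staff concern and urine output, and no pain score. Heart rate and respiration are still the only entries in it that the device supplies.

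**Step 2: is there a figure to reproduce?** No. The plan gives no duration, target or sample size for this endpoint. Everything below uses assumed values.

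**Step 3: how much of a difference could be content?** Set the complete manual time to 1. Let s be the share of it that a manual check of heart rate and respiration alone would need, including its own visit, entry and scoring. Let d be the digital time as a fraction of the complete manual time.

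- Apparent saving: 1 − d
- Like-for-like saving: s − d
- Part due to items not taken: (1 − d) − (s − d) = 1 − s
- Share of the apparent saving: (1 − s)/(1 − d)
- This share exceeds one half only when s < (1 + d)/2

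| s | d = 0 | d = 0.1 | d = 0.2 |
|---|---|---|---|
| 0.2 | 80% | 89% | 100% |
| 1/3 (equal time per item) | 67% | 74% | 83% |
| 0.5 | 50% | 56% | 62.5% |
| 0.6 | 40% | 44% | 50% |
| 0.7 | 30% | 33% | 37.5% |
| 0.8 | 20% | 22% | 25% |

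The share runs from 20% to 100% over this grid.

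**Step 4: why overhead must be separated.** Assume 6 minutes for a complete manual check, 1 minute for a digital check, and 1.5 to 2.5 minutes for measuring heart rate and respiration. The apparent saving is 6 − 1 = 5 minutes.

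- No shared overhead: the like-for-like saving is 1.5 − 1 = 0.5 to 2.5 − 1 = 1.5 minutes. The omitted-item share is (5 − 1.5)/5 = 70% to (5 − 0.5)/5 = 90%.
- If 2 of the 6 minutes are visit, entry and scoring, which a check of heart rate and respiration alone would also need: the like-for-like saving is (2 + 1.5) − 1 = 2.5 to (2 + 2.5) − 1 = 3.5 minutes. The share is (5 − 3.5)/5 = 30% to (5 − 2.5)/5 = 50%.

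One unrecorded quantity moves the answer from 70–90% to 30–50%.

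**Step 5: time that moves elsewhere.** Suppose half of the digital checks are followed by a manual round for the other items. That round takes 3.5 to 4.5 minutes under either case in step 4: 6 − 2.5 to 6 − 1.5 without overhead, or 2 + 1.5 to 2 + 2.5 if the overhead is incurred again. Average time is 1 + 0.5 × 3.5 = 2.75 to 1 + 0.5 × 4.5 = 3.25 minutes. The saving is then 6 − 3.25 = 2.75 to 6 − 2.75 = 3.25 minutes, instead of 5.

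**The case against.** The strongest reply is that the project replaces one ward routine with another, so timing each routine as delivered is a legitimate pragmatic question and equal content is not required. That is fair, but it does not rescue the endpoint as written. The new routine includes manual checks on request, and the plan does not say that their time is counted on the digital side. The word complete may also be meant to govern both checks, in which case the digital check might include them. That reading is possible, and it supports asking for a definition.

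A second reply is that the plan already collects spot checks per admission day per patient (7.a.ii) and total spot checks per admission (eCRF, 7.a.iii). Combined with time per check, these would give an approximate total. This stands in part, and the fix uses it. But the plan does not state such a combination, the eCRF does not list a count of digital checks, and a count does not show which parameters a check contained.

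Third, the endpoint is secondary and descriptive, with no decision rule. This stands and limits the priority.

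A reader might go further than the documents allow in three ways:

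- That most of the difference is omitted measurement. No durations are given, and step 4 shows that the answer turns on how visit, entry and scoring time is assigned.
- That the other parameters, including pain scoring, are dropped in phase 2. Blood pressure, saturation and temperature remain available on request, and nothing says that pain scoring stops.
- That a biased time will enter the cost evaluation. Section 7.a.ii bases costs on admission duration, admission costs and the monitoring method, and does not name the time measurement.

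**Conclusion.** The point holds in a limited form. The plan times two checks of different content, leaves one of them undefined, and does not say where requested phase 2 measurements are counted. An unknown and possibly large part of any time difference can therefore reflect measurements not routinely taken, or timed elsewhere, and not efficiency.

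The documents do not allow the share to be put at a figure. The range of about 20% to 100% rests on assumed s from 0.2 to 0.8 and d from 0 to 0.2. A majority follows under equal time per item, but not once a manual check of heart rate and respiration alone would take more than about half of the complete time. What is established is that the data as planned could not tell these cases apart. The change is worth making, at modest priority.

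**What to change.** Before phase 1 timing starts:

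1. Define the digital monitoring check: which staff actions start and end it, and whether a manual measurement requested because of it belongs to it.
2. When timing a manual check in either phase, record three parts separately (heart rate and respiration; all other parameters; shared overhead of visit, entry and scoring) and tick which parameters were taken.
3. Report (a) the digital check against the manual heart-rate and respiration part including the overhead that such a check would need.
4. Report (b), as the basis for any efficiency conclusion, total monitoring time per patient-day in phase 1 against phase 2. Phase 2 counts digital checks plus all manual checks actually added. The spot-check counts already planned supply the manual frequency; a count of digital checks per day has to be added.
5. State that complete manual against digital alone will not be read as time gained.

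The cost is slightly longer timing sessions and probably a smaller apparent saving. The attachments contain only the SUS, EBPAS and IWS, so the timing sheet has to be specified in any case. The phase 1 split matters most: patient records may later show which values were taken, but not how long each took. None of this takes a view on which vital signs should be measured.

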The medical research council (MRC) provided a document in 2000, the MRC model, to help researchers use the correct research designs, methods and measuring instruments (6). This model was revised in 2021 and forms the basis of the design of this project (6). This model structures the analysis using psychometric properties such as: acceptability, adoption, appropriateness, costs, feasibility, fidelity, penetration and sustainability (7).

Primary endpoints

Evaluation of the implementation of a continuous monitoring method on the surgical ward

- Fidelity: The usability and degree of implementation of the Healthdot at the surgical ward. Measured with the System usability scale (SUS), Score > 68 at M6 (8)
- Acceptability: The workload regarding the amount of spot checks in addition to the standard monitoring. Calculated with data from the electronic patient file records.
 Success in case of average reduction of 20% at M6 compared to M3

Secondary endpoints

- Adoption: The intention and attitude towards the use of the Healthdot monitoring method. Measured with evidence-based practise attitude scale (EBPAS)(9, 10).
- Feasibility: The extent to which the Healthdot monitoring method can be successfully carried out by the healthcare employees. Measured with a thematic analysis and input from the core group (Braun and Clark)(11)
- Acceptability: The workload regarding the amount of spot checks per hospital admission day per patient. Calculated with data from the electronic patient file records.
- Acceptability: The perception among nursing staff given the satisfactory and agreeableness regarding workload. Measured with the integrated workload scale (IWS) (12, 13).
- Appropriateness: Relation between device false alarms (noise) and correct alarms based on the alarming protocol. Measured as signal to noise ratio (SNR)
- Appropriateness: Number of unexpected events that occur during or result from the use of the Healthdot medical device. Measured as adverse device events (ADE)
- Feasibility: The amount of time needed to perform and process a complete manual spot check or digital monitoring check. Measured by manual time measurement.
- Costs: Cost-effectiveness analysis based on the duration of admission, the associated admission costs and the monitoring method. Calculation based on provided care and associated costs
- Algorithm improvement: Advanced algorithm analyses for improved monitoring protocols with use of artificial intelligence (AI)

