We hypothesize that the implementation of het Healthdot will be accepted and supported by the nursing staff and physicians since previous research has generated a positive attitude towards the use of the Healthdot in our hospital. Our assumption is that the attitude towards this change will shift towards an even more positive mindset during the implementation phase and that the training prior to this will have an important contribution. This change will be measured by the questionnaires, calculations and the Braun and Clarke thematic analysis. The device performance and signal-to-noise ratio and adverse device events will be analysed and are not expected to adversely affect the workability based on previous research.

These hypotheses will be accepted or rejected based on the outcome of this clinical investigation.

3. Project DESIGN

This project is designed as a 6-month monocentric prospective cohort at the Catharina hospital in the Netherlands. In the presently unlikely event that other sites will be included during the conduct of het study, amendments will be submitted to all respective internal and external approvers (ICBE, METC). Every patient admitted to the one surgery department during the duration of the study will receive a Healthdot as monitoring device. Implementation of the Healthdot as the new standard of care regarding monitoring will be performed stepwise in different phases: pre-condition phase, pre-implementation phase, implementation phase and maintenance and evolution.

During phase 1 (month 1-3) patients will receive the current standard monitoring method with manual spot checks and EWS. During this phase all healthcare staff involved will receive appropriate training regarding application of the device, reading and assessing the data and protocol explanation to optimize the infrastructure before implementation.

During phase 2 (month 4-6) patients will be monitored with the Healthdot primarily and receive additional manual spot checks if indicated. After these 6 months, the implementation will be evaluated and optimized and potentially extended.

[figure not shown]

Figure 1: Flowchart project design

Surgical	Month 1	Month 2	Month 3	Month 4	Month 5	Month 6
war	Spot check +	Spot check +	Spot check +	Healthdot	Healthdot	Healthdot
d	EWS	EWS	EWS			
Focus	Training	Training	Training	Implementation	Implementation	Implementation
	Infrastructure	Infrastructure	Infrastructure	Evaluation	Evaluation	Evaluation

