	Baseline data	Baseline data	Baseline data	Study data	Study data	Study data

Table 1: Overview focus during project phases

Objective	Instrument	0	1	2	3	4 (Switch)	5	6
Fidelity	SUS ^p					Q		Q
Acceptance	SC/day ^p				AD			AD
	SC/patient ^s				AD			AD
	IWS ^s	Q	Q	Q	Q	Q	Q	Q
Adoption	EBPAS ^s	Q			Q (9- 15)			Q
Appropriateness	SNR ^s							AD
	ADE ^s							AD
Feasibility	Thematic analysis ^s				FG		FG	FG
Time efficiency	Time measurement		М	М	М	Μ	Μ	М
Costs	Evaluation							AD

Q = questionnaire, AD = administered data, FG = focusgroep, M = manual measurement Table 2: Measurement timetable for psychometric properties

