Additional anonymized data will, in case of informed consent, be collected from the electronic patient file such age, gender, reason for admission, medical history, duration of admission, complications and laboratory results. This additional data will be used to relate the primary and secondary results to any influencing factors/ baseline characteristics and potentially correct for these factors.

Variables eCRF

Characteristic	Input
Indication	Open
Type of invasive interventions/surgery	Open
Gender	M/F
Age	Open
BMI	Kg/m2
Comorbidities	
Charlson comorbidity index	Charlson Comorbidity Index (CCI) - MDCalc
Hospital stay	
Admission date	D/M/Y
Discharge date	D/M/Y
Elective or emergency	Open
Complications	
Clavien-Dindo classification	Grade I-V
Complications type	Cardiac, Pulmonary, Kidney failure,
	infectious, traumatic, surgical related
	(perforation, leakage, bleeding)
Urgent consultations (SIT) during	0-99
hospitalization	
ICU admission	Yes/no
Mortality <30 days	Yes/no
Re-admission < 30 days	Yes/no
Fidelity	
Total minutes monitored	Min
Amount of heart rate measurements	Total number per admission
Amount of respiratory rate measurements	Total number per admission
Artefact heart rate measurements	Total number per admission
Artefact respiratory rate measurements	Total number per admission
Total amount of spot checks	Total number per admission
Device	
Premature removal of device	Yes/no
Replacement of device	Yes/no
Bijzonderheden device	Yes/no

b. Randomisation, blinding and treatment allocation

N/A

c. Project procedures

Prior to the start of the pre-implementation phase there will be a pre-implementation phase during months 1-2. This phase will consist of training the medical staff through e-learning and physical meetings. During this phase, medical staff will have the opportunity to apply the Healthdot, learn to activate it and practise with the Guardian dashboard. This phase serves as preparation for the implementation and aims to optimize the intra-structure in advance. In addition, during this phase, baseline data will be collected about the standard spot check measurements, feeling of confidence and attitude towards a change in the monitoring method. This study is a quality project and a change in standard of care. Nurses and physicians voluntarily participating in the focus group will sign informed consent for participation. Nurses not participating in the focus group but working at the surgical ward during this project will

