8. STATISTICAL ANALYSIS

The statistical analysis at professional (nurses/ physicians) level will be performed by means of descriptive statistics. Each continuous parameter is analyzed for normality by the Shapiro-Wilk test and visually by a figure. Normality-based reporting will be done using medians and interquartile ranges (IQR) or means and standard deviations (SD). Frequencies and percentages are reported for categorical data. Each continuous parameter is checked for normality by the Shapiro-Wilk test and visually by a figure. Normality-based reporting will be a figure. Normality-based reporting is performed using medians and interquartile ranges (IQR) or means and standard deviations (SD).

All analysis are performed using IBM SPSS Statistics 26.0 for Windows (IBM Armork, New York, USA) with 95% confidence interval and p < .05 as statistically significant.

The core group consisting of nurses, physicians and investigators will conduct a structured analysis into the fidelity, feasibility and acceptance of the implementation and this information is processed and objectified by means of a Braun and Clarke thematic analysis.

Objective	Instrument	Variable	Statistical test
Fidelity	SUS ^p	Continuous	Unpaired T-test/ Mann- Whitney U test
Acceptance	SC/day ^p SC/patient ^s IWS ^s	Continuous Continuous Ordinal	Descriptive statistics Descriptive statistics One-way ANOVA test
Adoption	EBPAS ^s	Continuous	Repeated measures ANOVA
Appropriateness	SNR ^s ADE ^s	Continuous Continuous	Descriptive statistics Descriptive statistics
Feasibility	Thematic analysis ^s	Nominal	Braun & Clarke thematic analysis
Time efficiency	Time measurement	Continuous	Descriptive statistics
Costs	Evaluation	Continuous	Descriptive statistics

Table 4: psychometric properties and statistical analysis

a. Other study parameters

N/A

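### The cost endpoint names no effect measure and would probably be summarised by medians, so it supports a before-after cost description, not a cost-effectiveness conclusion

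*Combined protocol and SAP*

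**What the plan says.** The Summary, Section 2 and Section 7.a.ii all list among the secondary endpoints a "Cost-effectiveness analysis based on the duration of admission, the associated admission costs and the monitoring method". The Summary adds "Calculation based on provided care and associated costs". Table 4 in Section 8 gives the whole analysis in one row: "Costs Evaluation Continuous Descriptive statistics".

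Section 8 contains one rule for summarising continuous data. "Each continuous parameter is analyzed for normality by the Shapiro-Wilk test and visually by a figure", and then "Normality-based reporting will be done using medians and interquartile ranges (IQR) or means and standard deviations (SD".

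The measurement timetable (Table 2 in Section 3) marks costs once, in the month 6 column, with a code explained as "AD = administered data". Section 3 also states: "After these 6 months, the implementation will be evaluated and optimized and potentially extended".

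The eCRF list in Section 7.a.iii has the field "Replacement of device", answered yes or no. Sections 6.a and 7.c give three reasons for a new device: no successful measurement after 4 hours, no connection within 60 minutes of application, and a stay longer than the battery life of about 14 days.

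**The concern.** A cost-effectiveness analysis sets a difference in cost against a difference in effect. Here length of stay drives cost, admission cost is cost, and monitoring method is what is compared. Nothing is left to serve as the effect. The eCRF collects complications, ICU admission, mortality and readmission, but no section links any of them to the cost analysis. Nor is there a perspective, a price source or a method for uncertainty.

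The summary statistic matters as well. What a hospital pays for a group of patients is the number of patients times the mean cost. Costs and stays are usually right-skewed, and a rule that then switches to the median answers a different question. Finally, the devices are part of the cost of the new method, and a yes/no field does not say how many were used.

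At stake is a published claim that the method is, or is not, cost-effective, which the planned analysis could not support in either direction.

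**Working it through.** The documents give no unit cost, cost spread, expected difference or power for this endpoint, so there is no stated figure to reproduce. The first step compares the text; the others are illustrations, and their assumptions are marked.

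**1. Is there an effect?**

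| Named input | Role |
|---|---|
| Duration of admission | Cost driver |
| Admission costs | Cost |
| Monitoring method | Comparator (phase 2 against phase 1) |

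No effect measure and no incremental comparison appear in the Summary, Section 2, Section 7.a.ii or Table 4.

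**2. Which summary would the rule select?** Inputs: 250 stays per phase (Section 4.d), or 900 / 4 = 225 from the lower turnover figure. Assumption: lognormal costs. In 1,000 simulated samples per setting, Shapiro-Wilk at the 5% level rejected normality as follows.

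| Log-SD (assumed) | n = 225 | n = 250 | Mean/median = exp(s²/2) |
|---|---|---|---|
| 0.2 | 88.7% | 91.2% | 1.02 |
| 0.3 | 99.6% | 100% | 1.05 |
| 0.5 | 100% | 100% | 1.13 |
| 0.8 | 100% | 100% | 1.38 |
| 1.0 | 100% | 100% | 1.65 |

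Even mild skew would nearly always lead to medians.

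**3. Can medians mislead?** Lognormal mean = median × exp(s²/2). All values are assumed, in arbitrary cost units.

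- Spread differs between phases. Phase 1: median 100, s = 0.8, mean 100 × exp(0.32) = 137.7. Phase 2: median 105, s = 0.65, mean 105 × exp(0.211) = 129.7. The median difference is +5 and the mean difference is −8.0.
- Spread is equal (s = 0.8 in both). The median difference is +5 and the mean difference is +6.9, so the sign agrees.

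A discrete example, also assumed: stays of 3, 4, 6 and 20 days in 30%, 35%, 25% and 10% of patients. The mean is 0.9 + 1.4 + 1.5 + 2.0 = 5.8 and the median is 4. If the longest stays fall from 20 to 14 days, the mean becomes 0.9 + 1.4 + 1.5 + 1.4 = 5.2 (−10%) and the median stays at 4.

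**4. How precise would a comparison of means be?** In the discrete example the variances are 57.3 − 5.8² = 23.66 and 36.9 − 5.2² = 9.86. With 250 per phase, SE = √((23.66 + 9.86) / 250) = 0.366. The 95% interval for the difference is −0.6 ± 1.96 × 0.366, or −1.32 to +0.12 days.

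**5. What does the yes/no field lose?** Assumption: replacements per stay are Poisson with mean λ. Devices per 100 stays are 100(1 + λ). The field implies 100(1 + 1 − exp(−λ)).

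| λ (assumed) | True | From yes/no | Undercount |
|---|---|---|---|
| 0.1 | 110 | 109.5 | 0.5 / 110 = 0.5% |
| 0.3 | 130 | 126 | 4 / 130 = 3% |
| 0.5 | 150 | 139.3 | 10.7 / 150 = 7% |
| 1.0 | 200 | 163.2 | 36.8 / 200 = 18% |

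**The case against.** Costs are one of several secondary endpoints. They have no success criterion, and neither hypothesis in Section 2 mentions them. That stands, and it limits the weight of the point.

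Section 8 opens at the level of nurses and physicians and allows means as well as medians, so medians for costs are not certain. This stands in part. However, the normality check is then applied to every continuous parameter, Table 4 labels costs continuous, and no other rule is given for them.

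The recommended comparison of means may also be inconclusive, as step 4 shows, and an unadjusted before-after difference mixes the device with case mix. Both stand, and the fix has to say so.

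Three stronger readings are tempting, and the documents do not support them.

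- *Costs are cut off at month 6 while late phase 2 patients are still in hospital, which would create a false saving.* The month 6 mark is not a data lock. It is the only cost entry, so it must cover phase 1 too. Evaluation is placed after the six months, and the eCRF collects 30-day mortality and readmission, which implies later collection. What remains is that no extraction date is given.
- *The number of Healthdots cannot be known.* Battery changes can be approximated from admission and discharge dates. The eCRF holds no cost field, so cost data must come from other records, and the documents do not rule out device records. What remains is that the eCRF field itself is not a count; repeat changes for failed measurement or connection cannot be recovered from it.
- *Any saving must sit in the longest stays, where a median misses it.* The primary hypothesis concerns nursing workload and efficiency, and such savings could shift the median. The discrete example in step 3 was built so that the median could not move; it shows what is possible, not what is likely.

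**Conclusion.** The concern holds for the label and the summary statistic. With no effect measure, no incremental comparison and descriptive statistics only, the endpoint can support at most a before-after cost description. This rests on the text alone.

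It is very likely, not certain, that costs and stay would be reported as medians: at least 99.6% of simulated samples were rejected at log-SD 0.3 or more, assuming lognormal costs and 225 to 250 stays per phase. Medians do not recover mean or total cost. They can miss or reverse a difference in means when the spread changes between phases, but they keep its sign when the spread is equal. These figures are illustrative, because the documents give no cost spread.

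The device field is a smaller matter. The undercount is negligible at low replacement rates and grows with repeat replacements, to about 18% at an assumed one replacement per stay. The extraction date is unspecified; no truncation bias is shown. The point is worth correcting before analysis, but it does not touch the primary endpoints.

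**What to change.** - Rename the endpoint *cost comparison per admission* and make no cost-effectiveness claim. Alternatively, name an effect measure and an incremental comparison.
- Report the phase 2 minus phase 1 difference in arithmetic mean cost and mean stay with a bootstrap 95% interval, whatever the normality test says. Medians and IQRs can be shown alongside as description.
- State that the interval may be wide and that a before-after comparison is open to differences in case mix. Add an analysis adjusted for the baseline data that Section 7.a.iii already collects for possible correction.
- Change the yes/no replacement field to the number of Healthdots used during the stay, and include device cost.
- As a clarification only, state that cost data are extracted after the last included patient is discharged.

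The price is some rewording, slightly more analysis, one changed eCRF field and a more modest label.
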